Comparative effectiveness of energy doses in critical illness

Short title: The Energy Dose Study

Principal Investigator: [name].

Protocol Version Date: 6/2/2014

NCT Number: NCT01369147

Abstract:

Protein and/or energy deficits are associated with increased rates of hospital infection, skeletal muscle weakness, impaired wound healing, and prolonged convalescence in ICU patients. To prevent or treat malnutrition, enteral nutrition (EN) and/or parenteral nutrition (PN) are routinely given worldwide to a significant proportion of ICU patients. Optimal caloric requirements in critically ill patients are unknown due to a lack of rigorous randomized clinical trials. The comparative efficacy of energy doses in critically ill patients is unknown and clinical recommendations are conflicting and controversial; this issue is the focus of our study.

We have designed this pilot, single-center Randomized Clinical Trial (RCT) to prospectively compare, for the first time, the clinical efficacy of different energy doses in ICU patients requiring PN due to intestinal failure/dysfunction. A total of 60 patients will be studied (20 per energy dose group) to generate critical preliminary data needed to inform subsequent appropriately powered Phase III multicenter trials.

The primary aim of this study is to perform a controlled, double-blind, prospective, randomized, intent-to-treat Phase II clinical trial to test the efficacy of three specific energy doses [0.6, 1.0 and 1.3 x measured REE (resting energy expenditure), respectively], given for 28 consecutive days during the ICU course, on 28-day total hospital-acquired infections (primary endpoint), Blood Stream Infections (BSI), and other important clinical outcomes in medical/surgical ICU patients requiring specialized parenteral \pm enteral feeding. We would also determine, in these subjects A) the impact of cumulative and mean daily 28-day energy deficits [energy intake-measured REE] on clinical outcome endpoints; and B) the practical utility of estimated REE determined by Harris-Benedict equation versus measured REE across different energy doses. We would also like to determine the impact of administered energy dose and energy deficits on global metabolomic patterns over time and their association with key clinical outcomes.

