cardiac death⁴⁵⁻⁴⁹. Fractal analysis of metabolomic data will allow us to test whether the Hurst exponent is related to clinical outcomes and/or response to nutritional interventions in the ICU patients we propose to study.

Emerging data strongly suggest that microbes of the intestine (the microbiota) play a key role in host metabolism, immune/inflammatory processes and disease pathophysiology⁵⁰⁻⁵². The intestinal microbiome (genome of the gut microbiota) is shaped by both environment (e.g. diet) and host genetics; and, vice versa, the gut microbiota itself appears to regulate a wide spectrum of host immune, inflammatory and metabolic responses⁵³. **Human data on the impact of nutrition support during critical illness on the gut microbiome are limited.**

Despite limited evidence, there is a suspected interplay between critical illness and the gut microbiome, which warrants further exploration in the setting of nutrition support⁵⁴⁻⁵⁸. Nelson et al utilized 16S rRNA pyrosequencing to characterize stool of hospitalized patients and observed perturbations in gut microbiota following infection⁵⁹. It is acknowledged that the microbiome plays an integral role in health maintenance, and that modifications of the gut microorganisms may influence outcomes in critically ill patients.

Hypothesis:

- 1) Adequate energy administration (defined as 1.3 x REE) will result in a lower 28-day total hospital-acquired infection rate compared with ICU patients receiving lower energy doses.
- 2) Differences in energy intake will result in global changes in metabolic patterns that themselves are associated with clinical outcomes in the ICU patients studied.

Specific Aims:

- 1) To perform a controlled, double-blind, prospective, randomized, parallel group, intent-to-treat Phase II clinical trial to test the efficacy of three specific energy doses [0.6, 1.0 and 1.3 x measured REE (metabolic cart), respectively], given for 28 consecutive days during the ICU course, on 28-day total hospital-acquired infections (primary endpoint), BSI, and other important clinical outcomes in medical/surgical ICU patients requiring specialized parenteral ± enteral feeding.
- 2) In Aim 1 subjects to: a) examine the impact of cumulative and mean daily 28-day energy deficits [energy intake-measured REE] on clinical outcome endpoints; and b) to estimate the agreement for REE as determined by the HBE and the measured REE across different energy doses.

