High-resolution metabolomics analysis: Plasma samples will be obtained at baseline and on days 3, 7, 14, 21 and 28 after entry (please see study schema above). Metabolomic profiles at the specific analysis time-points will be compared to compare subjects: 1) within the three study energy doses; 2) whom develop a nosocomial infection or a BSI versus those who do not; and 3) who die compared to those who are alive at 28 days. Samples will be analyzed in triplicate with a Thermo LTQ-Velos Orbitrap high-resolution mass spectrometer (\geq 50,000 resolution) following extraction with acetonitrile containing an internal standard mixture and separation on anion exchange and C18 columns. Validated extraction methods (apLCMS and xMSanalyzer) ^{44, 62} will be used to provide a mass/charge ratio (m/z) feature table of detected ions, characterized by relative retention time and accurate mass. The mass spectrometer will be set to collect data from m/z ratio 85 to 2000 daltons over a 10-minute chromatography period. Internal stable isotopic standards are spiked into every sample so that the relative retention time and accurate mass provide unambiguous denotation of an ion even if the chemical is unidentified ⁶³; relevant reference samples are included preceding and following each block of 20 samples for long-term quality assurance. Electrospray ionization will be used in the positive ion mode for detection. When necessary, tandem mass spectrometry will be used to positively identify metabolites of interest, with a metabolite defined as any chemical in a biological system.

Stool sampling and gut microbiome analysis: On study days 0, 3, 7, and 14 the primary nurse will collect a small sample of stool (\pm 24-hr window of each study day). All specimens will be collected into sterile containers, processed, and stored at -80°C as previously outlined ⁶⁴. The

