For Aim 2: The agreement between the study entry HBE and the initial REE, as well as the mean daily serial MREE by metabolic cart, will be summarized using graphical methods and by calculating the 95% limits of agreement estimated by the mean difference ± 1.96 standard deviation of the differences. Bland and Altman (1999)⁶³ extend the limits of agreement approach to data with repeated measurements (i.e., serial REE measurements). To investigate whether the relationship between mean daily serial REE and entry HBE is altered by the mean daily caloric dose administered, regression methods will be used (i.e., analysis of covariance, ANCOVA). ANCOVA analyses will also be stratified by location (ICU versus the floor).

For Aim 3: The data processing will be performed as follows: 1) Feature detection conducted by systematic re-extraction with multiple parameter settings that optimize sensitivity and reliability; 2) Sample quality and feature consistency evaluation; 3) Feature overlap detection between datasets; 4) Statistical analysis includes false discovery rate (FDR; typically with $q=0.05$) to identify significantly different features between the two groups while correcting for multiple comparisons; hierarchical cluster analysis (HCA) to visualize differences between groups as

well as between time points and to identify clusters of highly correlated features that can be mapped to biological pathways; 5) Characterization of features and biological pathways utilizing multiple chemical databases (KEGG) metabolic pathways

(http://www.genome.jp/kegg/tool/color_pathway.html), MetaCore (www.genego.com; Carlsbad, CA), and MetaCyc (<http://www.metacyc.org>).⁶⁹ We will utilize Metaboanalyst 2.0⁷⁰ for the time series analysis to detect metabolic changes throughout the study period and two-way ANOVA to determine the impact of varying energy doses on global metabolomics patterns. Once important features have been identified, we have the ability to positively identify the chemical names of known metabolites by MS/MS analysis.

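### The metabolomic comparisons by infection and by death name no energy-arm or severity term, so features that only track dose (post-baseline) or illness severity can be reported as outcome markers

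*Combined protocol and SAP*

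**What the plan says.** The High-resolution metabolomics analysis section lists three comparisons: "Metabolomic profiles at the specific analysis time-points will be compared to compare subjects: 1) within the three study energy doses"; subjects "whom develop a nosocomial infection or a BSI versus those who do not"; and those "who die compared to those who are alive at 28 days". Plasma is taken at baseline and on days 3, 7, 14, 21 and 28.

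Under Statistical Analysis, For Aim 3, the feature-level step is FDR control, typically at q = 0.05, "to identify significantly different features between the two groups while correcting for multiple comparisons". Cluster analysis, pathway mapping and a time-series analysis follow. The one metabolomic model that names dose is a "two-way ANOVA to determine the impact of varying energy doses on global metabolomics patterns".

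Hypothesis 2 reads: "Differences in energy intake will result in global changes in metabolic patterns that themselves are associated with clinical outcomes". Hypothesis 1 predicts fewer infections at 1.3 x REE than at the lower doses. The section on parenteral and enteral nutrition explains that the arms differ in infused carbohydrate and lipid. APACHE II (15 or below, or above 15) is a randomisation stratum.

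Covariate models are described for clinical endpoints under Aim 1: a GEE Poisson model for infections, and a multivariable logistic model for mortality with APACHE as a candidate factor. Metabolite features appear in neither.

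**The concern.** Under the trial's own two hypotheses, energy arm is a common cause of metabolite levels and of infection. A feature that responds to the infusate but has no relation to infection within any arm will then still differ between infected and uninfected patients when the arms are pooled. FDR control does not correct this. It limits chance findings, whereas here the pooled association is real and only its interpretation is wrong.

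Severity acts in the same way and needs no arm effect. Sicker patients may have both a different metabolome and a higher risk of death or infection, so severity markers can appear as outcome markers even at baseline.

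At stake is the reading of Hypothesis 2, which is about patterns that are themselves associated with outcome. A pooled contrast cannot tell such a pattern from a bystander of dose or severity. The Background suggests that future nutritional strategies could be built on the specific metabolites found, so a misread marker could steer later work.

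**Working it through.** **1. Which model goes with which question**

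| Comparison | Model named | Arm term | Severity term |
|---|---|---|---|
| By energy dose | two-way ANOVA | yes | none named |
| Infection/BSI vs none | group contrast with FDR | none named | none named |
| Dead vs alive at day 28 | group contrast with FDR | none named | none named |

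The ANOVA asks what dose does to the metabolome, not which features go with outcome.

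**2. Inputs.** From the Abstract: "A total of 60 patients will be studied (20 per energy dose group", and 3 x 20 = 60 agrees. The documents state no power, effect size or event rate for the metabolomic analysis, so there is no figure to reproduce. Assumed:
- infection risks across 0.6/1.0/1.3 x REE of 50/40/30% or 60/45/30%;
- a feature unrelated to infection within arms, with residual SD 1 and arm means proportional to dose, differing by d = 1, 2 or 3 SD between the extreme arms;
- all 60 patients sampled.

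**3. Expected spurious difference.** The arm means are d x (0, 0.571, 1), because (1.0 - 0.6)/(1.3 - 0.6) = 0.571. With equal arms and risks p, the infected mean is sum(p x mean)/sum(p), and the uninfected mean uses 1 - p.
- 50/40/30%: infected (0.40 x 0.571 + 0.30)/1.20 = 0.440; uninfected (0.60 x 0.571 + 0.70)/1.80 = 0.579. Difference -0.14 d.
- 60/45/30%: infected (0.45 x 0.571 + 0.30)/1.35 = 0.413; uninfected (0.55 x 0.571 + 0.70)/1.65 = 0.615. Difference -0.20 d.

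Over d = 1 to 3 the size runs from 0.14 to 0.61 SD. With equal risks it is zero.

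**4. How often this is reported.** Simulation with 20 per arm. For the FDR columns, 1,000 independent features were assumed, 100 of them pure dose markers and none truly related to outcome, with Benjamini-Hochberg at q = 0.05 and 1,000 runs.

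| Infection risk | d | Nominal p < 0.05 | Any dose marker passes FDR | Mean number reported, of 100 |
|---|---|---|---|---|
| 50/40/30% | 1 | 7% | 1.9% | 0.02 |
| 50/40/30% | 2 | 12% | 5.0% | 0.18 |
| 50/40/30% | 3 | 17% | 4.2% | 0.66 |
| 60/45/30% | 1 | 11% | 3.9% | 0.06 |
| 60/45/30% | 2 | 22% | 10.0% | 0.68 |
| 60/45/30% | 3 | 32% | 14.0% | 2.98 |

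Repeat runs move these by about a percentage point or two. With a wider spread of 60/40/20%, at least one dose marker passes in about 10 to 36% of runs. With 40/40/40% the nominal rate is 5.1 to 5.4%, and any marker passes in at most 0.9% of runs. With arm in the model the nominal rate is about 5% in every setting, and any marker passes in at most about 1% of runs.

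**5. Severity and death.** Same design, with patients split 30/30 by severity and 100 features that mark severity only. The share of a feature's variance explained by severity was assumed to be 0.25 or 0.50.

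| Mortality, low/high stratum | Nominal p < 0.05 | Any severity marker passes FDR |
|---|---|---|
| 20/20% | 5.0 / 4.9% | 0.4 / 0.6% |
| 10/30% | 16.2 / 27.2% | 7.4 / 11.7% |
| 10/40% | 26.7 / 49.8% | 18.6 / 37.6% |

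The paired figures are for 0.25 / 0.50. With stratum in the model, the nominal rate is 4.9 to 5.0% and any marker passes in at most 0.8% of runs.

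**The case against.** **The plan is silent; it does not rule adjustment out.** The metabolomics section lists who is compared, not a model, and the Aim 3 text is a general pipeline in which the two groups are not defined. This stands: the accurate statement is that covariates are not specified. But the text as written permits the unadjusted analysis and asks for nothing else.

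**FDR decides what is reported, and it limits the damage.** This stands for size. In the tabulated scenarios, 86 to 98% of runs report no dose marker. A reader who took the nominal 7 to 32% as the reporting rate would overstate the problem.

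**The dose mechanism is narrower than it may look.** A reader might infer that all three outcome comparisons at all time points can pick up infusate markers. The documents do not support that. Baseline samples precede study PN. The Potential Risks section knows of no data suggesting that ICU mortality differs between the doses, so for death severity is the confounder with a documented basis. The same section calls the evidence on morbidity conflicting, so the infection mechanism depends on Hypothesis 1 being true.

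**The dose comparison already shows which features respond to dose.** A feature on both the dose list and the infection list can be recognised as suspect. That helps, but overlap of lists does not show whether the feature is related to infection within arms.

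**Adjustment changes the question.** Hypothesis 2 describes a path from intake to metabolic pattern to outcome, and conditioning on arm removes the between-arm part of a true mediator. This stands, and is why the unadjusted comparison should be kept beside the adjusted one.

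**Conclusion.** The point holds, with conditions. No arm or severity term is specified for the infection, BSI and death comparisons, and the ANOVA that names dose does not fill the gap.

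For post-baseline samples and infection, bystander dose markers can be reported if dose affects infection: in about 2 to 15% of runs under the FDR rule at the two main assumed risk patterns, more if risks differ more, and not above the error rate if risks are equal. For all samples, including baseline and the death comparison, severity markers can be reported whenever severity predicts outcome.

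The sizes rest on assumed event rates, effect sizes, 1,000 independent features with 100 markers, and complete sampling. None of these is in the documents. Correlated features, a different share of markers or fewer late samples would change the figures.

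A reader might go further and conclude that most reported outcome markers would be artefacts, or that the trial's main result is compromised. Neither follows. Aim 3 is exploratory work in a 60-patient pilot, and what is affected is the interpretation of candidate markers, not the primary endpoint.

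**What to change.** In the High-resolution metabolomics analysis section and in the Aim 3 part of Statistical Analysis:

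- Base outcome-marker claims for infection, BSI and death on feature-level linear models with the outcome group as the term of interest. Include APACHE II stratum as a covariate at every time point, and energy arm as well for post-baseline samples.
- Apply the q = 0.05 FDR to the p-values of the outcome term.
- Keep the unadjusted comparison as a labelled descriptive result, and state that it cannot by itself separate a mediator from a marker of dose or severity.

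The cost is analysis work only, because arm and APACHE II are recorded for every patient. Each post-baseline model uses three more degrees of freedom (two for arm, one for stratum): with all 60 patients sampled, residual degrees of freedom fall from 60 - 2 = 58 to 55. Baseline models use one.

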standardized CRFs. The primary endpoint is total nosocomial infection rate during the 28-day study period. Secondary Aim 1 post-entry endpoints to be monitored include: 1) 28-day hospital mortality; 2) Rate of new nosocomial blood stream infections (BSIs) during the initial 28 days; 3) Rate of new nosocomial infections during the initial 28 days; 4) mean ICU SOFA score; 5) ICU ventilator-free days at day 28; 6) ICU and total hospital length of stay.

Hospital nutrition support - Administration of double blind parenteral and enteral nutrition:

Briefly, the nutritional goals are to provide total daily calorie (kcal) intake [from PN + dextrose-containing IV fluids (> 500 mL/day) + propofol/clevidipine + any enteral feedings) at 0.6, 1.0 or 1.3 x baseline MEE (per metabolic cart). We will then serially adjust total PN/EN energy dosing based on real-time serial cart REE measurements during the ICU stay, as indicated by the energy dose group to which the patient is randomized. The total amino acid/protein intake goal is 1.2 g/kg/day. Dextrose will initially comprise 70% of PN non-amino acid kcal and IV fat (30% Intralipid[®]) 30% of PN non-amino acid kcal daily, adjusted as clinically indicated. The 1.0 x REE energy dose study group will serve as the control group in this CER study. Study PN will be continued only if deemed indicated by the investigators and the primary physicians. Daily intake of study PN volume (mL), PN dextrose (g), PN lipid emulsion (g), intake of study tube feeding volume, and daily PN and enteral (oral or tube feeding) volumes will be calculated and entered into the CRFs daily for the initial 28 days after entry, beginning on day 1.

Study subjects will receive a maximum of 28 days of double blind study PN ± EN. Subjects will be transitioned from PN to enteral feeds as soon as tolerated and clinically indicated. Study PN will be discontinued when enteral intake of \geq 50% of energy requirements is achieved for \geq 48 hr. The amount of PN administered will be decreased as a function of actual enteral nutrient intake to maintain daily goals. The 24-hr daily study PN will be prepared under sterile laminar air flow hood conditions by the unblinded research pharmacist and pharmacy technician at each site. The study EN will be made in the Metabolic Kitchen or in the compounding area of the pharmacy.

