Data and Safety Monitoring Board (DSMB): The Data and Safety Monitoring Board (DSMB) will act in an advisory capacity to the National Institute of Diabetes, Digestive and Kidney Diseases (NIDDK) to monitor subject safety and evaluate the efficacy of the intervention being studied in this clinical trial funded by the NIDDK. The DSMB will be appointed by the PIs upon study funding, and approved by NIDDK program staff. The DSMB will be composed of at least two experienced clinical nutrition support investigators not otherwise participating in the study and not affiliated with Emory. A biostatistician not otherwise participating in the study will also be named to the DSMB. The DSMB will meet twice yearly, and as needed, and will receive blinded and unblinded reports on study progress prepared by the DCC.

Statistical Analysis:

Continuous variables will be summarized with standard descriptive statistics and represented graphically with displays such as scatterplots, box plots, line plots and histograms, while categorical variables (adverse events) will be described by frequency tables.

For Aim 1: The primary analyses of the data will be performed according to subjects' original treatment assignment (i.e., intention-to-treat analyses) and the inclusion of all data from all subjects randomized in the final analysis. Rates of infection (i.e., BSI and total nosocomial infections) per 1000 hospital days will be estimated overall and for each of the 3 energy doses. Confidence intervals (95%) for the incidence rates will be estimated using an exact method based on the Poisson distribution.

Additionally incidence rates of infection will be estimated by performing a generalized estimating equations (GEE) Poisson regression analysis of the counts, implemented using SAS Proc Genmod, using an exchangeable correlation structure for the repeated counts within subject. The incidence rate ratio (IRR) is the ratio of the incidence density in one group to that of another group. Results by each baseline covariate will be presented as the IRR and the 95% confidence interval (CI). This GEE model can also accommodate time-dependent covariates such as daily blood glucose levels measured before an infection and total 28-day energy (cumulative deficit or as a time-dependent covariate).

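### The metabolomic comparison by infection does not separate samples drawn before onset from those drawn after it, and the comparison by death runs out of deaths at the later sampling days

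*Combined protocol and SAP*

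**What the plan says.** The section on high-resolution metabolomics analysis sets the schedule: "Plasma samples will be obtained at baseline and on days 3, 7, 14, 21 and 28 after entry". It continues: "Metabolomic profiles at the specific analysis time-points will be compared to compare subjects". Three contrasts follow: the energy doses, patients "whom develop a nosocomial infection or a BSI versus those who do not", and patients "who die compared to those who are alive at 28 days".

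Infection is counted over the same period as the sampling. Under the serial data entry heading: "The primary endpoint is total nosocomial infection rate during the 28-day study period". The events are new infections after entry.

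For Aim 3, the Statistical Analysis section gives false discovery rate control "to identify significantly different features between the two groups while correcting for multiple comparisons", clustering, and "time series analysis to detect metabolic changes throughout the study period and two-way ANOVA". It does not say whether infection status is fixed over the 28 days or updated at each draw, whether post-onset samples are used, or how patients who died before a draw are handled. For Aim 1, by contrast, the infection model can take "time-dependent covariates such as daily blood glucose levels measured before an infection".

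**The concern.** Both outcome groupings are defined by events that occur while the samples are being collected. A patient infected on day 8 would, on the ever/never reading, contribute a day-14 sample to the infected group although that sample reflects established infection. A difference at day 14 then mixes what came before infection with what infection did to metabolism.

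The distinction matters for the use the protocol foresees. Its second hypothesis has energy intake altering metabolic patterns that are in turn associated with outcome, and the Background foresees future nutritional strategies built on metabolites associated with better outcomes. A metabolite that moves only after infection starts is a poor candidate for a strategy to prevent infection.

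The death comparison has a different problem. A sample cannot follow death, so the direction of effect is not in doubt in the same way. But patients who died before a draw give no sample, so the group of deaths changes from one sampling day to the next and shrinks towards zero.

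**Working it through.** The documents state no sample size, power or event rate for these comparisons, so there is no figure to reproduce. The inputs from the documents are the sampling days, the 28-day event window and the 60 patients. Event proportions, onset timing and effect sizes are assumptions, shown as ranges.

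**1. Share of eventually infected patients whose sample at day t falls on or after onset.**

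- Constant hazard with proportion R infected by day 28: (1 − exp(−ht))/R, with h = −ln(1 − R)/28. For R = 0.3, h = 0.01274, and at day 14 the share is (1 − exp(−0.1783))/0.3 = 0.163/0.3 = 54%.
- Uniform onset: t/28.
- Exponential onset with mean m, truncated at day 28: (1 − exp(−t/m))/(1 − exp(−28/m)).

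| Assumed timing | Day 3 | Day 7 | Day 14 | Day 21 | Day 28 |
|---|---|---|---|---|---|
| Uniform | 11% | 25% | 50% | 75% | 100% |
| Constant hazard, R = 0.3 | 12% | 28% | 54% | 78% | 100% |
| Constant hazard, R = 0.5 | 14% | 32% | 59% | 81% | 100% |
| Exponential, mean 14 days | 22% | 46% | 73% | 90% | 100% |
| Exponential, mean 7 days | 36% | 64% | 88% | 97% | 100% |

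At baseline the share is 0% in every row, because only new post-entry infections count. The 100% at day 28 is automatic, because the event window closes there.

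**2. What that can do to a comparison.** These shares measure exposure to the problem, not bias, so an illustrative simulation was run. It used 60 patients, 30% or 50% infected, uniform onset, and a feature with no relation to later infection that shifts by 0.8 or 1.5 SD after onset. Each setting had 3,000 runs with a two-sided t-test at 0.05 for a single feature. It does not model the planned false discovery rate procedure.

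| Probability of declaring a difference | Baseline | Day 3 | Day 7 | Day 14 | Day 21 | Day 28 |
|---|---|---|---|---|---|---|
| Ever vs never, 30% infected, 0.8 SD | 0.05 | 0.06 | 0.11 | 0.30 | 0.52 | 0.79 |
| Ever vs never, 50% infected, 1.5 SD | 0.04 | 0.08 | 0.25 | 0.71 | 0.97 | 1.00 |

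Restricting each day to patients not yet infected, and comparing those infected later with those never infected, gave 0.040 to 0.056 at baseline and days 3 to 21 across all settings (runs with fewer than three cases were left out). No day-28 comparison is possible under that rule.

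**3. Deaths available to the died-versus-alive comparison.** With D deaths spread uniformly over 28 days, D(1 − t/28) can still be sampled at day t. For an assumed 20% mortality, D = 0.20 × 60 = 12, which leaves 9 at day 7, 6 at day 14, 3 at day 21 and 0 at day 28. For mortality of 10% and 30% (D = 6 and 18), day 21 has 1.5 and 4.5. Draws are scheduled between 0800 and 1000 h, so a death later on day 28 could still count. Hence essentially none, rather than strictly none.

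**4. Cases left after the restriction.** With 30% of 60 infected (18 patients) and constant hazard, 18 × (1 − 0.544) = 8.2 cases remain at day 14 and 18 × (1 − 0.782) = 3.9 at day 21, before deaths and missing samples.

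**The case against.** The strongest reply is that Aim 3 is exploratory and worded throughout as association. Describing how infected and uninfected patients differ is a legitimate aim even when some samples follow onset, and a post-onset difference is a real one. That stands. A reader might infer that the plan intends to report metabolites as predictors of infection. The documents do not support this: they never call metabolites predictors, and the biomarkers mentioned in the Background are of energy insufficiency and response to dose. What can be said is that results could be misread, because the two kinds of sample are not kept apart.

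The plan is also silent on how infection status is assigned at each draw. Grouping by ever or never infected is the natural reading, not a stated rule, so the defect is unspecified timing. The silence still needs filling, since the Aim 1 model shows that the order of measurement and infection was considered for glucose.

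A reader might also carry the reverse-causation argument over to the death comparison. It does not apply there. Loss of early deaths limits precision and changes which deaths are compared, but an empty day-28 group cannot produce a false finding.

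Finally, restriction costs cases. With so few left at day 21 and error control across a full feature table, later comparisons may detect little. That is true, and it is a reason to rest the main comparison on early samples.

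**Conclusion.** The point holds as an unspecified timing rule in an exploratory analysis. Neither the false discovery rate control nor the time-series methods address temporal order. On the ever/never reading, the post-onset share of the infected group's samples is about 11% to 36% at day 3, 25% to 64% at day 7, 50% to 88% at day 14, 75% to 97% at day 21 and 100% at day 28. These ranges rest on assumed onset timings, and the simulated rejection rates also rest on assumed effect sizes. That the shares rise from zero at baseline to all samples at day 28 does not depend on those choices.

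The death comparison has a separate limitation: later days include only late deaths, and day 28 has essentially none.

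Nothing here supports the inference that the trial's main result is at risk. The primary endpoint and the baseline metabolomic comparison are unaffected. This is a cheap improvement.

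**What to change.** Add a short paragraph to the Aim 3 analysis:

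- **Infection comparison.** At each sampling day, include only patients with no new post-entry infection before that sample. Cases are patients whose first new infection comes after the sample and by day 28. Apply the same rule to BSI onset for the BSI comparison. Omit day 28. Report post-onset samples separately, as response to infection.
- **Death comparison.** At each sampling day, include everyone alive at the sample, whatever their infection status; an infection-free requirement would discard deaths that follow infection. Cases are deaths after the sample and by day 28. Omit day 28.
- **Both.** Report the numbers at risk and of cases at each day, and treat baseline and early samples as the main outcome comparison.

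No new data should be needed. Patients are monitored daily on case report forms, and using glucose measured before an infection in Aim 1 already requires onset dates. The cost is few cases at later days: about 8 at day 14 and 4 at day 21 under the assumptions shown.
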